7.2 Inclusion Criteria

1. Subjects must have a subjective memory concern as reported by subject, study partner or clinician.
2. Meets ADNI criteria for diagnosis of MCI ⁵². Subjects with amnesic (single or multi-domain) will be eligible, as both subtypes of MCI are at high risk for progression to AD.
3. Abnormal memory function documented by assessment using the Logical Memory subscale (Delayed Paragraph Recall, Paragraph A only) from the Wechsler Memory Scale-Revised (the maximum score is 25):
 - (a) <11 for 16 or more years of education
 - (b) <9 for 8-15 years of education
 - (c) <6 for <7 years of education
4. Mini-Mental State Exam score between 24 and 30 (inclusive). Exceptions may be made for subjects with less than 8 years of education at the discretion of the PI.
5. Clinical Dementia Rating = 0.5. Memory Box score must be at least 0.5.
6. General cognition and functional performance sufficiently preserved such that a diagnosis of AD cannot be made by the physician at the time of the screening visit.
7. Cholinesterase inhibitors and memantine are allowable if stable for 12 weeks prior to screen.
8. Stability of Permitted Medications for 4 weeks. In particular, subjects may washout from excluded medication for at least 4 weeks prior to screening.
9. Geriatric Depression Scale (GDS) \leq than 6.
10. Male or female outpatients aged 50-90 (inclusive).
11. Study partner has regular contact with the subject adequate to provide a reliable assessment of the subject's level of function, and can be available for all clinic visits, either in person or by telephone, for the duration of the study.
12. Visual and auditory acuity adequate for neuropsychological testing.
13. Good general health with no diseases expected to interfere with the study.
14. For women of child-bearing potential (i.e., one who is biologically capable of becoming pregnant), must be willing to use a medically acceptable form of birth control or practice abstinence for the duration of her participation in the trial. Acceptable methods of birth control include: oral or patch contraception, or medroxyprogesterone (Depo-Provera®) or other intramuscular contraceptive injection, or implantation of levonorgestrel (Norplant®) system, an IUD, a reliably-employed barrier method (e.g. diaphragm, cervical cap or condom), or a male partner who is surgically sterilized.
15. Modified Rosen Hachinski \leq 4.
16. Completed six grades of education or has a good work history (sufficient to exclude mental retardation).
17. Able to communicate in English with study personnel.
18. Able to understand the nature of the study and must provide written informed consent prior to conduct of any study procedures.
19. Willing to undergo repeated MRIs (3Tesla) and at least three PET scans. No medical contraindications to MRI.
20. Agrees to blood collection for APOE and biomarker testing.
21. Agrees to lumbar puncture over the course of the study for the collection of CSF.

CSF levels of Ab42, total Tau, and Tau phosphorylated at threonine 181 consistent with underlying AD pathology according to established threshold values at Emory and the ADNI Biomarker Core

7.3 Exclusion criteria

1. Any significant neurologic disease other than MCI and suspected incipient AD, such as Parkinson's disease, multi-infarct dementia, Huntington's disease, normal pressure hydrocephalus, brain tumor, progressive supranuclear palsy, poorly controlled seizure disorder, subdural hematoma, multiple sclerosis, or history of significant head trauma followed by persistent neurologic deficits or known structural brain abnormalities.
2. Screening/baseline MRI scan with evidence of infection, large vessel infarction or other focal structural lesions that could account for the memory deficits. Subjects with multiple lacunes or lacunes in a critical memory structure are excluded.
3. Contraindication to MRI due to presence of pacemakers, aneurysm clips, artificial heart valves, ear implants, metal fragments or foreign objects in the eyes, skin or body, or excessive weight.
4. Presence of clinically significant suicide risk, based on the Investigator's judgment informed by a structured clinician interview. Any suicide attempt within the past 1 year of the screening visit is exclusionary.
5. Major depression, bipolar disorder as described in DSM-IV within the past 1 year, or history of schizophrenia (DSM-IV). Psychotic features, agitation or behavioral problems within the last 3 months which could lead to difficulty complying with the protocol.
6. History of alcohol or substance abuse or dependence within the past 2 years (DSM-IV criteria).
7. Allergic to any component of atomoxetine (Strattera).
8. Any uncontrolled medical condition that is expected to preclude completion of the study, or any medical condition which would represent a contraindication to atomoxetine pharmacotherapy (e.g. hepatic insufficiency, untreated hypertension, untreated cardiovascular or cerebrovascular disease).
9. Known serious structural cardiac abnormalities, cardiomyopathy, serious heart rhythm abnormalities, or other serious cardiac problems.
10. History of narrow angle glaucoma.
11. History of pheochromocytoma.
12. Clinically significant abnormal findings on screening laboratory tests or physical exam. Abnormalities in Vitamin B12 level, TFTs or LFTs that might interfere with the study. A low Vitamin B12 level is exclusionary, unless follow-up labs (homocysteine and methymalonic acid indicate that it is not physiologically significant).
13. Women who are pregnant or lactating, or who plan to become pregnant during the study.
14. Current use of warfarin (exclusionary for lumbar puncture).
15. Inability to obtain initial CSF sample.
16. Use within 60 days of a monoamine oxidase inhibitor .
17. Current use of anti-psychotic medication.

18. Current use of the following anti-depressant medications that act on NET: duloxetine, venlafaxine, desvenlafaxine, imipramine, or amitriptyline.
19. Current participation in another clinical trial. Participation in clinical studies involving neuropsychological measures being collected more than one time per year.
20. CSF profile is not consistent with underlying Alzheimer's Disease pathology.
21. Reasonable likelihood for non-compliance with the protocol or any other reason, in the opinion of the investigator, prohibits enrollment of subject into the study.
22. Exceptions to these guidelines may be considered on a case-by-case basis at the discretion of the protocol director.

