1.1 Preclinical studies have identified a surprising but powerful role for locus coeruleus (LC) and NE in AD pathogenesis. Extensive LC degeneration is nearly universal in AD⁷⁻¹¹, among the earliest pathologies¹²⁻¹⁴, and it has long been known that decreased NE is linked to cognitive, mood and neuropsychiatric symptoms¹⁵⁻²⁰. However, recent studies show that LC dysfunction in AD animal models also plays a direct causal role in pathogenesis, with NE loss accelerating amyloid deposition and neuron death via pleiotropic effects on chronic inflammation, neurotrophin expression, cerebral metabolism, cholinergic neurons, and blood brain barrier permeability, in addition to deleterious effects on cognition – recapitulating key aspects of AD²⁰⁻²⁷. These effects of decreased NE levels have been confirmed and extended in several independent laboratories and lines of AD mice^{21,23-25,28}. Thus, combining LC lesions with expression of familial AD mutations more closely recapitulates the neuropathological and cognitive symptoms of AD than mutant APP expression alone, and implicates LC loss as a crucial component of AD.

1.2 Neuroinflammation is a key mechanism linking loss of LC neurons and NE innervation with AD. Recent studies provide insights into the mechanisms by which LC dysfunction and NE loss contribute directly to AD pathogenesis. Major targets of NE include microglia, astrocytes, and endothelia, which in healthy conditions acts through β -adrenergic receptors to suppress the expression of multiple pro-inflammatory genes, including major histocompatibility complex class II, tumor necrosis factor- α , interleukin-1 β , and the

inducible nitric oxide synthase^{29,30}. Furthermore, NE is critical for the expression of anti-inflammatory molecules such as nuclear factor kappa B (NF-kappaB) inhibitory I kappa B proteins, and of heat shock protein (HSP70)³¹. Heneka et al.²⁷ demonstrated that in APP23 transgenic mice, but not wildtype mice, LC lesion profoundly increased A β plaque load, brain inflammation, and spatial memory deficits. These effects of diminished NE levels were mediated by impaired microglial phagocytosis and clearance of A β , and a switch in microglial cytokine expression from a neuroprotective anti-inflammatory profile to a pro-inflammatory and neurotoxic profile^{24,26,27}.

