1.4 Previous Human Experience Atomoxetine appears to be safe in the elderly, and has the potential to prevent, slow, or even reverse disease progression. We believe that atomoxetine, an FDA-approved NET inhibitor that is a safe and widely prescribed treatment for children and adults with ADHD, is the best choice among currently available pro-noradrenergic drugs to test in MCI. Atomoxetine has high affinity and selectivity for the NET (Ki for reuptake inhibition *in vitro* = 1.9 nM for NET vs. 750 nM for SERT and 1600 for DAT). It has very weak affinity for adrenergic, dopaminergic, histaminergic, serotonergic,

and cholinergic receptors that are typically blocked by first generation tricyclic reuptake inhibitors (e.g., desipramine) ⁴⁶.

A few studies have examined atomoxetine in elderly patients with neurodegenerative disease to assess safety, tolerability and symptomatic effects. Marsh et al ⁴⁷ studied 12 patients with Parkinson's Disease (PD) with doses up to 100 mg daily (mean tolerated dose 89.6 mg), with excellent safety, tolerability, and improved executive function. Weintraub and colleagues ⁴⁸ found that 80 mg once daily was well tolerated by PD subjects as a treatment for depression; only 4 of 29 withdrew because of adverse effects. A 6-month phase II trial in mild to moderate AD tested up to 80 mg once daily in 47 subjects, and only 5 of them withdrew because of adverse effects ⁴⁹.

The proposed Phase IIa, double-blind, placebo-controlled, 6 month crossover study will examine the effect of atomoxetine in 40 subjects with MCI. The primary outcome will be CSF biomarkers of inflammation and their relationship to effects on noradrenergic function. We will also explore rates of change in biomarkers of neurodegeneration (A β , tau, brain atrophy rates), and collect data on safety and symptom progression. Collectively, these results will inform design of a larger phase II multi-center trial application to the NIH within 2 years time.

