12.7 NET Occupancy. In the absence of data from PET studies allowing definitive knowledge of NET occupancy as a function of drug dose, an *ex vivo* assay established in the laboratory of [name], will use serum to estimate NET occupancy. Serum samples will be used to directly measure inhibition of active [³H]-monoamine transport in cells expressing the human serotonin, norepinephrine or dopamine transporters. Uptake measured in drug-free baseline serum is compared to that observed in the subject's samples while on drug and expressed as both % baseline uptake and % occupancy. These assays are sensitive to free drug concentrations representative of extracellular space within the brain where transporter inhibition is hypothesized to be correlated with therapeutic efficacy.

12.8 MRI. Brain MRI scan will be obtained or reviewed at screening to verify eligibility, at baseline, at 6 months and after 12 months of treatment or placebo, using protocols adapted from the ADNI study as described below.

MRI films performed clinically within the past two years will be reviewed by the investigators for eligibility in the study. If a subject does not have clinical MRI films available, the MRI will be performed and reviewed prior to performance of the LP for safety reasons and to ensure that the subject meets eligibility criteria.

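### Exclusion 18 is a closed list that omits desipramine, and no visible criterion or analysis addresses beta-blockers, so the mechanism test may lose sensitivity by an unknown amount

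*Combined protocol and SAP*

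**What the plan says.** Sections 1.3 and 1.4 make CSF inflammatory markers the primary outcome, as a test of how norepinephrine (NE) is thought to work. Section 1.2 gives the route: NE "acts through β -adrenergic receptors to suppress the expression of multiple pro-inflammatory genes".

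The rules on other medication are in sections 7.2 and 7.3:

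- Exclusion 18: "Current use of the following anti-depressant medications that act on NET: duloxetine, venlafaxine, desvenlafaxine, imipramine, or amitriptyline". It names five drugs, with no wording such as "including" or "for example".
- Exclusion 8 gives as examples of contraindicating conditions "untreated hypertension, untreated cardiovascular or cerebrovascular disease". Treated hypertension is not barred, and the age range is 50 to 90.
- Inclusion 8 requires "Stability of Permitted Medications for 4 weeks" and lets candidates wash out from excluded drugs. The visible text does not list the permitted medications.

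Desipramine appears once, in section 1.4, in a sentence about "cholinergic receptors that are typically blocked by first generation tricyclic reuptake inhibitors (e.g., desipramine").

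Section 12.7 defines NET occupancy by a within-patient comparison: "Uptake measured in drug-free baseline serum is compared to that observed in the subject's samples" taken on drug.

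Section 8.31.2 records all medications. Section 7.5 stratifies on APOE4 and CSF biomarkers only. Section 10 plans chi-square or Fisher tests, Wilcoxon tests and Spearman correlations, with no analysis by co-medication.

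**The concern.** The trial tests a chain: inhibit NET, raise NE, act on beta-adrenergic receptors, lower inflammation. A drug that already acts on NET could blunt the first step, and a beta-blocker could blunt the third. Exclusion 18 shows that the sponsor saw the first risk, but its wording does not cover the whole class it describes. Nothing visible in the plan covers the second risk, either at entry or in the analysis.

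What is at stake is how a negative result is read. This pilot is meant to inform a larger trial. If some participants had little chance of showing the effect, a null finding in 34 completers would be harder to read as evidence against the mechanism. A participant already on a reuptake inhibitor at baseline would also have NET occupancy measured against uptake that was already reduced.

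**Working it through.** **Inputs.** Section 4.2 gives 40 randomised, 15% drop-out and 34 completers. Section 7.5 gives 1:1 allocation, so 34 / 2 = 17 per arm. Section 4.2 assumes 80% worsening on placebo and states 87.7% power. Section 10 names the chi-square or Fisher test. Alpha is not stated; I assume 0.05, two-sided.

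**Reproducing the plan's figure.** Power is the sum, over all pairs of counts (a, b) with Fisher p ≤ 0.05, of Bin(a; 17, 0.80) × Bin(b; 17, p₂).

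- With p₂ = 0.25 worsening on atomoxetine, power is 87.8%, which matches the stated 87.7%.
- Read literally, section 4.2 has 25% *not* worsening, so p₂ = 0.75 and power is about 2.7%. That wording is a separate matter. I use p₂ = 0.25 because it reproduces the stated figure.

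**Dilution.** Let a fraction f of atomoxetine patients worsen at the placebo rate. Then p₂(f) = 0.25(1 − f) + 0.80f = 0.25 + 0.55f.

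| f (assumed) | p₂ | Fisher power, 17 per arm |
|---|---|---|
| 0% | 0.250 | 87.8% |
| 5% | 0.2775 | 83.4% |
| 10% | 0.305 | 78.2% |
| 20% | 0.360 | 66.0% |
| 30% | 0.415 | 52.3% |

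At f = 10%, 0.10 × 17 = 1.7, or about two atomoxetine patients.

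The table assumes no response at all in affected patients. If they keep half the effect, p₂ = 0.25 + 0.275f. Power is then 83.4%, 78.2% and 72.4% at f = 10%, 20% and 30%.

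**What a repeat in non-users could show.** Suppose the share f applies in both arms and the full 80% vs 25% effect holds in non-users. The arms shrink to 17 × 0.9 ≈ 15, 17 × 0.8 ≈ 14 and 17 × 0.7 ≈ 12. The same enumeration gives 78.5%, 74.6% and 71.6%. The diluted full set gives 78.2%, 66.0% and 52.3% at the same f.

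**The case against.** Several objections have weight.

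- **Dilution is a possibility only.** The documents give neither the share of users nor the degree of blockade. A reader might infer that a patient on a beta-blocker cannot respond. The text does not support that: section 1.2 also describes NE effects on IκB proteins and HSP70 without naming a receptor, and how far any beta-blocker blocks the relevant brain receptors is not discussed. This stands, so the figures above are a sensitivity range.
- **The desipramine gap is probably small in practice.** Major depression within a year is excluded, GDS must be at most 6, and exclusion 21 leaves room for investigator judgement. Section 1.4 calls desipramine a reuptake inhibitor in a sentence about receptor blockade and does not say outright that it acts on NET. This limits the likely numbers, but the list still falls short of its own purpose.
- **The drug-free baseline may simply mean before study drug.** A stable co-medication would then be in both samples. That is a fair reading. Even so, the measure for such a patient would start from an altered reference.
- **The randomised comparison is not biased.** Stable use unrelated to assignment costs sensitivity only, although chance imbalance is possible at 17 per arm.
- **A null result would not be uninterpretable.** NE metabolites, drug levels and NET occupancy are measured, and medications are recorded. This stands.
- **Part of the text is missing.** The protocol between sections 4.4 and 6 was not available for review, so a medication rule there cannot be ruled out.
- **Admitting patients on stable treatment is a legitimate choice in a pilot of this age group.** I agree.

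**Conclusion.** The point holds as a gap between the stated mechanism and the rules that should protect its test. Exclusion 18 does not cover the class it describes, and neither the visible criteria nor section 10 deals with beta-blockers. The result may be a loss of sensitivity of unknown size. Under an assumed 10% to 30% of atomoxetine patients with no response, power falls from 87.8% to between 78.2% and 52.3%. With none affected, nothing is lost. These figures rest on the assumed f, complete loss of effect in those patients, two-sided alpha 0.05, 17 per arm, and 25% read as the worsening rate on atomoxetine.

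A reader might go further and infer that the mechanism test is in fact diluted, or that beta-blocker users ought to be excluded. The documents establish neither. Exposure and degree of blockade are unknown, and exclusion would trade recruitment and generality for a benefit that cannot be sized.

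**What to change.** 1. **Section 7.3, exclusion 18.** Reconcile the wording with its stated purpose: describe the class of medications that act on NET and give the named drugs as examples. The sponsor should then confirm where desipramine falls, and check how the wider wording interacts with the washout provision in inclusion 8.
2. **Section 10.** Add one sentence: as a supportive analysis, the Week 29 inflammatory comparison will be repeated, with the same Fisher and Wilcoxon tests, in participants not recorded as taking a beta-blocker at baseline. No new model is needed, and the medication data are already collected. Report the number of users in each arm beside it.

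The cost is one eligibility line, one analysis sentence and possibly a few candidates. The supportive analysis will be small (about 12 to 15 per arm at the assumed shares) and less powerful than the main comparison was planned to be, so it can inform a null result but not settle it. No change to any patient's treatment is proposed.

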7.4 Patient Numbering

Patients who have signed the informed consent form to begin screening procedures will be assigned a Subject Identification Number at that time. The Subject Identification Number will consist of the 3-digit study number (001) followed by a 3-digit subject identifying number. The patient will keep the same number throughout the study; a separate randomization number will not be provided at Baseline.

7.5 Randomization

Subjects will be assigned a randomization number as above. To achieve balanced patient groups, subjects will be randomly assigned on a 1:1 basis in a blinded fashion to atomoxetine or placebo treatment during the initial phase, stratified based on APOE4 results (carrier or non-carrier), and CSF biomarkers for high or low. To accomplish this, the biostatistician will use blocks of size 2 and provide a computer generated randomization to the Alzheimer's Disease Cooperative Study group and the Investigational Drug Service.

When ordering study medication, the study coordinator will receive a blinded subject assignment number, via the Alzheimer's Disease Cooperative Study Group. An identical subject assignment legend will be held in safe and confidential custody in a sealed envelope by the Investigational Drug Service.

Manual Randomization Plan

The study biostatistician will keep a copy of randomization scheme and will be on call. The Investigational Drug Service will also have a copy of the randomization scheme and will serve as back-up for the study biostatistician if the biostatistician is not available. When a subject meets the eligibility criteria and informed consent has been signed, the study biostatistician will inform the study coordinator and pharmacist the randomization assignment code for the subject based on the randomization plan.

Mis-Randomization Plan

There are two scenarios in mis-randomization, i.e., the patient is ineligible and randomized, or the patient is assigned to wrong treatment. Considerable care should be taken to avoid mis-randomization. If the participant is ineligible and randomized, we must subsequently withdraw that participant from the study and classify them as a mis-randomization, the patient should be included in the baseline analysis and treated as withdrawn. If the patient

is assigned to wrong treatment group, the patient should remain in the group randomized and be included in the analysis based on the “intent-to-treat” (ITT) principle. Secondary analysis can be performed according to patient’s actual treatment and compared to the ITT analysis.

Unblinding

In the event that it becomes medically imperative to know what the subject is receiving, the investigator will contact the Investigational Drug Service to determine. Date and reason for disclosure must be documented. If possible, the investigator will confer with the safety officer before unblinding.

8. STUDY ASSESSMENTS AND PROCEDURES

The study design and assessment schedule are presented in Table 1.

8.1 Informed Consent. The study will be discussed with the study subject and appropriate others (family, study partner) and if they are interested in learning more about the study they will be provided with a copy of the informed consent form to review in detail. The study subject will be contacted at a later date to determine if they would like to be screened for possible participation in the study. If they are interested, a screening visit will be made. Potential subjects are encouraged to discuss participation in these studies with their family or physician prior to screening for the study. In addition they are encouraged to contact the office with any questions or concerns.

At the time of the screening visit the consent form will again be reviewed with the study subject and appropriate others, questions will be answered and if they are still interested in study participation the consent will be signed. Ample opportunity will be given to respond to any questions and provide requested information regarding the study. After all questions are answered to participant and study partner satisfaction, the consent is signed.

This study includes subjects who must score between a 24 and 30 on the MMSE (Mini Mental Status Examination) and will therefore be experiencing mild cognitive impairment as a result of their Alzheimer's disease. Individuals with mild impairment will likely be able to provide informed consent however it should not be assumed that all subjects have the capacity to consent based only on an MMSE score. Capacity for consent will also be determined by the study subject’s ability to engage in a discussion regarding the study and their ability to understand what will be involved in study participation. The individual obtaining consent will review and discuss the research project and the consent document with the potential study participant and their family/study partner/legally authorized representative and will decide if they are able to understand the nature of the research, appreciate the experimental nature of the study, and understand the potential risks as well as alternatives to study participation.

In the event that the subject is not competent to provide consent, assent is obtained. A study subject’s legally authorized representative will be present during the initial consenting process. Signed consent will be obtained from all study subjects. The same process described previously will be employed in obtaining legally authorized representative’s consent, when deemed necessary. Consent will be obtained prior to conducting any screening assessments or procedures.

8.2 Screening Phase. The following tasks will be performed at the first screening visit (1a):

- Subjects will sign a written informed consent prior to the performance of any study-related procedures.
- The eligibility of the subject to participate in the trial will be assessed by a comprehensive evaluation. Patients that appear to be eligible will be administered the
 - Mini Mental Status Exam (MMSE),
 - Logical Memory (LM) and
 - Clinical Dementia Rating-Sum of Boxes (CDR-SB) assessments.
 - Geriatric Depression Scale (GDS)

Those participants who do not meet criteria for amnesic MCI will be excluded from participation. Patients meeting criteria for amnesic MCI (single or multi-domain) without any exclusionary diagnoses will complete:

- Medical history, including review of medications
- Physical and neurologic exams
- Blood pressure, heart rate, respiratory rate, temperature
- Height and weight
- ECG
- Modified Rosen Hachinski
- Suicidality assessment
- Urinalysis
- Blood work:
 - CBC
 - Comprehensive metabolic panel
 - TSH
 - Vitamin B12 level
 - Coagulation panel
 - Blood work for APOE
 - Serum pregnancy test (for women of child-bearing potential).

If safety laboratory tests and ECG are consistent with protocol eligibility at the second screening (1b), the tasks below may be performed on the same day, or may be performed on separate days. Screening 1b will occur within one calendar month of screening 1a.

- If pre-enrollment MRI is not available at the time of screening, the baseline MRI will be completed and reviewed prior to screening lumbar puncture (LP) to determine eligibility. Pre-enrollment MRI completed no more than two years prior to screening may be used for review.
- Blood work
 - Inflammatory biomarkers
 - Metabolomics

- Primary Panel for Inflammation, Oxidative, and Nitrosative Stress
 - Norepinephrine metabolites (catecholamines)
 - Pax Gene
- Salivary amylase
- If the subject has had a clinic LP within 6 months prior to the date of visit 1b and CSF has been banked for research purposes, no screening LP will be performed. The banked CSF will be used for analysis. In all other cases, an LP will be performed by an MD or NP following an overnight fast. CSF will be assessed for the following:
 - Glucose
 - Protein
 - Cell count with differential
 - A β 42, tau, phospho tau
 - Inflammatory Biomarkers
 - NE Metabolites (catecholamines)
- Contact subject on the day after LP to inquire about new adverse events.

8.3 Baseline Visits. The baseline visit will occur within 1 calendar month of Screening visit **1b**. Patients that continue to meet eligibility requirements will undergo the following test at visit **2A**:

- MRI performed at the Emory Center for Systems Imaging **if not performed as part of the screening visit.**
- FDG PET Scan

Visit 2b will consist of the following tests/procedures:

- Interim history review
- Concomitant medication review
- Adverse event review
- Suicidality assessment
- Confirm continued eligibility
- Blood pressure, heart rate, respiratory rate, temperature
- Weight, physical and neurologic exams
- American National Adult Reading Test (ANART)
- Montreal Cognitive Assessment (MoCA)
- Category Fluency (Animals)
- Trails A & B
- Boston Naming Test (30 item)
- Auditory Verbal Learning Test
- Clock drawing
- Neuropsychiatric Inventory IQ
- ADAS-Cog 13 (with Delayed Word Recall and Number Cancellation)
- Activities of Daily Living (FAQ)
- Blood work

- Serum atomoxetine level
- NET occupancy
- Blood work for future research (per individual subject consent)
- Randomization to drug or placebo
- Study drug dispensed
- Subjects will be directed to take their daily pill in the AM after breakfast to prevent nausea.

